9.2 Definition of baseline and change from baseline

Baseline is defined as the non-missing assessment reported at index date (Baseline visit).

Absolute and percent changes from baseline are defined as

$$\text{absolute change} = \text{visit value} - \text{baseline value}$$

$$\text{percent change} = 100 * (\text{visit value} - \text{baseline value}) / \text{baseline value}$$

9.3 Study day / study treatment day

Day 1 is the index date, the day before is Day -1 (no Day 0 is defined). Study day / Study treatment day is defined relative to Day 1.

9.4 Definition of duration and ‘time since’ variables

Durations in days will be calculated by the difference of start and stop date + 1 if not otherwise specified.

The time since an event (eg, time since first diagnosis) will be calculated as reference date minus date of event.

9.5 Conversion factors

The following conversion factors will be used to convert days into months or years:

1 week = 7 days, 1 month = 30.4375 days, 1 year = 365.25 days.

9.6 Date of last contact

The date of last contact will be derived for participants not known to have died at the analysis cut-off using the latest complete date prior to or at the data cut-off date among the following:

- All participant assessment dates (visit date, dates of assessment for vital signs, disease assessment as per imaging, NCCN-FACT FKSI-19)
- AE start and end dates
- Study drugs start and end dates
- Date of discontinuation on the Avelumab and/or Axitinib Termination or Study Termination eCRF pages (do not use if reason for discontinuation is lost to follow-up).

For PFS, PFS2 and DoR, a patient progressing after stopping current treatment and starting a new therapy will be censored at the latest tumor assessment showing no progression before changing therapy.

Only dates associated with actual examinations of the participant reported in the eCRF will be used in the derivation. Dates associated with a technical operation unrelated to participant status will not be used. Assessment dates after the cut-off date will not be applied to derive the last contact date.

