**Table 1. Schedule of Assessments**

Assessment	Screening visit	W0 (Index date/ Baseline visit)	Follow-up visits (between W0 to W104) as per routine clinical practice	W104 (end of study)
Informed consent	X			
Inclusion/exclusion criteria	X	X		
Demographics (year of birth, gender)		X		
Physical examination/ vital signs a		X		
Body weight a		X	X	X
Concomitant diseases b		X		
Concomitant medications c		X	X	X
Cancer history d		X		
ECOG performance status		X		
MSKCC risk group e		X		
IMDC risk group f		X		
HRQoL using the NCCN-FACT Fksi-19 questionnaire g		X	X	X
Safety assessment	X	X	X	X
Avelumab plus Axitinib therapy h		X	X	X
Second-line treatment (if Avelumab plus Axitinib discontinued)			X	X
Third-line treatment (if second-line treatment discontinued)			X	X
Treatment response i			X	X
Treatment for AE related to Avelumab plus Axitinib therapy j		X	X	X

AE=Adverse event, ECOG=Eastern Cooperative Oncology Group, HRQoL=health-related quality of life, IMDC=International Metastatic RCC Database Consortium, MSKCC=Memorial Sloan-Kettering Cancer Center, NCCN-FACT Fksi-19=National Comprehensive Cancer Network/Functional Assessment of Cancer Therapy-Kidney Symptom Index 19, W=Week

a Results from physical examinations, vital signs, and body weight will be collected upon availability. Physical examination includes an examination of major body systems. Vital signs include blood pressure (systolic and diastolic) and pulse rate.

b Information on concomitant diseases such as autoimmune disease, cardiovascular disease, hypertension, renal failure, and liver disease.

c Information on concomitant medications such as the use of corticosteroids, anticoagulants, and antibiotics.

d Information on cancer history: age at diagnosis, tumor, node, metastasis (TNM) stage, location of metastases, received nephrectomy, other prior cancer therapies and procedures, expression of the programmed death ligand 1 (PD-L1).

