14.1 Primary Endpoint: Overall Survival Rate at 12 Months

14.1.1 Primary Objective: Derivation and Analysis of the Primary Endpoint: Overall Survival Rate at 12 Months

Endpoint Derivation

OS Rate at 12 months	OS rate is defined as the percentage of patients who are alive at 12 months after the index date. OS rate will be presented along with 95% CI. Percentage of patients alive at the time of outcome assessment (12 months) will be calculated as per the KM approach.
-----------------------------	--

[REDACTED]
[REDACTED]
[REDACTED]
[REDACTED]
[REDACTED]
(collected in “[REDACTED]” eCRF page)

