14.2 Further Endpoints

Endpoint Derivations

OS Rate at 24 months	OS rate is defined as the percentage of patients who are alive at 24 months after the index date. OS rate will be presented along with 95% CI.
-----------------------------	--

	Percentage of patients alive at the time of outcome assessment (24 months) will be calculated as per the KM approach.
OS	
OS is defined as the time from index date to the date of death due to any cause. OS for participants without death prior to cut-off will be censored at date of last contact. OS in months is calculated as follows:
 $\text{OS (months)} = [\text{date of death or censoring} - \text{index date} + 1] / 30.4375$ 
Note: If death events occurring after cut-off are to be taken into account, the table below may be used for OS. Nevertheless, this will not be the standard process.
 
OS will be estimated by the KM method. The percentage of censored patients will also be reported. Median event time will be reported, along with 25th and 75th percentiles. Percentage of patients experiencing event or being event-free at applicable timepoints will also be reported along with the corresponding two-sided 95% CIs.
 
Analyses of overall survival time

PFS	
PFS time is defined as the time from index date to the date of the first documentation of objective PD or death due to any cause, whichever occurs first. The tumor response will be determined according to Response Evaluation Criteria in Solid Tumours (RECIST) v 1.1 and assessed by the investigator.
 $\text{PFS time (in months)} = (\text{Date of PD or death} - \text{index date} + 1) / 30.4375 \text{ (months)}$

PFS data will be censored on the date of the last adequate tumor assessment for participants who do not have an event (PD or death) or start a subsequent anti-cancer therapy prior to an event. Participants who do not have any post-baseline tumor assessments will be censored on the start date.

The last adequate tumor assessment is defined as the last tumor assessment result that is not “NE” or “NA”.

The censoring and event date options to be considered for the PFS analysis is presented in below table.

PFS will be estimated by the KM method. The percentage of censored patients will also be reported. Median event time will be reported, along with 25th and 75th percentiles. Percentage of patients experiencing event or being event-free at applicable timepoints will also be reported along with the corresponding two-sided 95% CIs.

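### SAP 9.6 leaves later-line therapy dates out of the date of last contact and contradicts its own list, so some living patients can be censored too early in the primary OS analysis

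*SAP*

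**What the plan says.** SAP 14.1 defines the primary estimate: "Percentage of patients alive at the time of outcome assessment (12 months) will be calculated as per the KM approach". SAP 14.2 sets the event and censoring rules. For the event, "OS is defined as the time from index date to the date of death due to any cause"; for everyone else, "OS for participants without death prior to cut-off will be censored at date of last contact". Nothing ties a death to the date of last contact. Deaths up to the cut-off count, and counting deaths after the cut-off is described as non-standard.

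SAP 9.6 takes the latest complete date, up to the cut-off, from four sources:
- assessment dates (visits, vital signs, imaging, FKSI-19);
- adverse event start and end dates;
- study-drug start and end dates;
- "Date of discontinuation on the Avelumab and/or Axitinib Termination or Study Termination eCRF pages", unless the reason is loss to follow-up.

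It then states: "Only dates associated with actual examinations of the participant reported in the eCRF will be used in the derivation". The following sentence excludes dates of technical operations that say nothing about the participant's status.

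Subsequent anti-cancer therapy is not in the list, but it is collected. Protocol Table 1 has rows for second-line and third-line treatment at follow-up visits and at week 104. SAP 12 summarises subsequent therapy from its own eCRF page, and SAP 9.9 has an imputation rule for its start date.

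**The concern.** There are two defects. First, a recorded second-line start or stop date shows that the patient was alive on that day, yet the rule may censor the patient before it. Second, adverse event, study-drug and termination dates are not examinations, so the examinations sentence conflicts with the list above it. Two programmers could derive different censoring dates for the primary endpoint.

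The gap matters most after treatment stops, because most listed sources then run out. FKSI-19 collection ends with treatment (Protocol 9.2.4). The mandatory AE recording period ends 90 days after discontinuation or at 24 months, whichever is first (Protocol 11.4). Study-drug dates cease. Vital signs are taken at baseline only (SAP 15.4). Visits, imaging and study termination remain. Visit timing follows routine practice, and a patient still in the study at the primary analysis has no study termination date yet.

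At stake is the independence of censoring in the primary endpoint. If living patients leave the risk set early while deaths in similar patients are still recorded, the Kaplan-Meier rate falls below the true rate.

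**Working it through.** The visible documents give no expected OS rate, precision or censoring proportion, so there is no figure of the plan's own to reproduce.

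**Inputs from the documents.** About 100 patients (Protocol 9.5); recruitment over about 24 months (Protocol 9.1.1); primary analysis once the last patient reaches 12 months (SAP 6.1).

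**Assumptions.**
- True 12-month OS of 78.3% to 89.9%, with 85% between. The ends are the two one-year rates that Protocol section 7 quotes for sunitinib and for pembrolizumab plus axitinib.
- Time on treatment is exponential with a median of 13.8 months, the median PFS quoted there for avelumab plus axitinib. The share off treatment by month 12, ignoring deaths, is then 1 − 2^(−12/13.8) ≈ 45%.
- f is the share of off-treatment patients with no listed date after stopping. pd is the probability that a later death in such a patient is still recorded. The death hazard after stopping is 1 or 3 times the on-treatment hazard. The documents give none of these.

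**Step 1: closed form.** Take 100 patients and D deaths before month 12, all recorded. Let c living patients be censored before those deaths. The Kaplan-Meier product telescopes to S = 1 − D/(100 − c), against 1 − D/100 with full follow-up.

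| D | full follow-up | c = 5 | c = 10 | c = 20 |
|---|---|---|---|---|
| 10 | 90.0% | 89.5% | 88.9% | 87.5% |
| 15 | 85.0% | 84.2% | 83.3% | 81.3% |
| 22 | 78.0% | 76.8% | 75.6% | 72.5% |

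For example, 1 − 15/90 = 83.3%. Having every censoring precede every death makes these large values for a given c.

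**Step 2: the sign.** Take 15 true deaths and 10 patients censored early, x of whom later die unrecorded. Then S = 1 − (15 − x)/90. With x = 0 it is 83.3%. With x = 1.5, the same death rate as everyone else, it is 1 − 13.5/90 = 85.0%, so no bias. With x = 3 it is 1 − 12/90 = 86.7%, which is too high.

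**Step 3: simulation.** 1,500 trials of 100 patients, with uniform 24-month accrual, cut-off 12 months after the last patient and exponential death times. Off-treatment patients who keep having recorded visits are seen at most 3 months apart. The table gives bias in the 12-month rate in percentage points, over the three true rates and both hazard ratios.

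| f | pd | bias |
|---|---|---|
| 0 | 1 | −0.02 to −0.05 |
| 10% | 1 | −0.2 to −0.4 |
| 25% | 1 | −0.6 to −1.0 |
| 50% | 1 | −1.2 to −2.1 |
| 100% | 1 | −2.7 to −4.8 |
| 25–50% | 0.5 | −1.1 to +0.4 |
| 25–50% | 0, equal hazard | about 0 |
| 25–50% | 0, threefold hazard | +0.6 to +2.6 |

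These figures compare the rule with complete follow-up. Adding therapy dates recovers only part of the difference, because it moves censoring no further than the last therapy date.

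**Step 4: scale.** The exact 95% CI for 85 of 100 is 76.5% to 91.4%, a half-width of (91.4 − 76.5)/2 ≈ 7.5 points.

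**The case against.** The strongest reply is that the list is not confined to the treatment period. Visit, imaging and study termination dates count whenever they occur, and patients stay in follow-up after stopping treatment (Protocol 9.1.1, 9.2.3, 9.2.5). The primary analysis waits until everyone could have 12 months of follow-up, so only living patients whose last listed date falls before month 12 matter. This stands: with continuing visits the simulated bias is at most 0.05 points.

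It can also be said that Table 1 records later-line therapy at visits, so a therapy date will seldom be later than a visit date that already counts. This largely stands. The omission bites when therapy is entered from medical records, which the Protocol abstract names as the data source, without a matching later visit or scan. How often that happens cannot be read from the documents.

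The examinations sentence may be meant only to keep out technical dates, as the sentence after it suggests. That is plausible and supports rewording it.

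A reader might go further and infer that the primary OS rate is biased downward as a matter of course. The documents do not support that. The direction requires near-complete capture of deaths after the last listed date, and follow-up also ends at withdrawal or loss to follow-up (Protocol 9.2.3). A reader might also infer that telephone or registry survival contacts are collected and then discarded. No such collection is described.

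Text between SAP 14.1.1 and 14.1.3 is blacked out, and the OS outcome table announced in 14.2 is not visible. Either could bear on this point; neither is counted here as a gap.

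**Conclusion.** The point holds as a defect in a stated rule. SAP 9.6 omits collected dates that prove survival, and its restriction contradicts its own list. Followed as written, it can censor a living patient before a recorded known-alive date and so bias the Kaplan-Meier OS rates.

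At 12 months the likely size is about 0 to 2 points: downward when later deaths are captured, smaller or upward when they are not, and near zero when post-treatment visits are recorded. Larger values, up to about 5 points, need every off-treatment patient to have no later listed date while all deaths are known, which is an extreme case. All of this rests on the assumed f, pd, hazard ratio and time on treatment. The 24-month rate follows the same censoring rule; its bias was not calculated.

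The effect is small beside a CI half-width of about 7.5 points in a descriptive study. It is still worth correcting, because the interval does not reflect a systematic error and the correction costs almost nothing.

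**What to change.** In SAP 9.6, add complete start and stop dates of subsequent anti-cancer therapy, up to the cut-off, to the list, together with any other known-alive date already recorded in the eCRF. Use non-imputed dates only: SAP 9.9 moves a start date with a missing day to the end of the month (unless the therapy ended earlier), which could place a patient alive later than is known.

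Reword the examinations sentence so that it excludes only technical or administrative dates, such as data-entry dates. It then agrees with the adverse event, study-drug and termination dates in the list.

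The cost is a change of SAP wording and a small change to one derivation before database lock. No new data collection is needed.

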9.7 Time window

As this is a non-interventional study, study assessments are part of the standard of care and related data will be collected during the visits in line with the sites as per routine practice at the discretion of the treating physician. Therefore, the timing of the visits is an approximation.

Baseline data will be collected at the index date. The Screening visit and the Baseline visit may or may not be on the same day.

Patients will attend the sites (hospitals) as per routine clinical practice at the discretion of the treating physician. Therefore, the timing of the visits may vary.

Apart from Screening, Baseline visit (index date) and HRQoL, analysis visits will be derived considering a 3 months (\pm 45 days [as intermediate timepoint between 2 consecutive visits]) frequency and will be calculated using study day as showed in table below.

Visit Name	Derivation
Screening	Screening ^a
Baseline	Index date/W0 (Baseline visit) ^a
3 Months	45 days ^b \leq STUDY DAY \leq 135 days
6 Months	136 days \leq STUDY DAY \leq 225 days
9 Months	226 days \leq STUDY DAY \leq 315 days
12 Months	316 days \leq STUDY DAY \leq 410 days
15 Months	411 days \leq STUDY DAY \leq 495 days
18 Months	496 days \leq STUDY DAY \leq 585 days
21 Months	586 days \leq STUDY DAY \leq 675 days
24 Months	676 days \leq STUDY DAY \leq 765 days

^a Screening and Baseline visits will not be remapped as they are the starting of the observation. Both will be assigned as per eCRF visit

^b In case a follow-up visit will occur in period between Baseline visit and 44 days after the index date, analysis visit settings will be discussed to identify the best mapping.

Patients will be asked to provide HRQoL data using the NCCN-FACT FKSI-19 questionnaires available as electronic patient-reported outcomes (ePRO) questionnaires at the index date and at every 6 weeks thereafter, until the EOT or end of 24 months of study follow-up period, whichever occurs first. For the ePRO collected during the study all the data in a time window of \pm 14 days from the expected visit day will be used.

ePRO Assessment	Derivation
Baseline	Index date/W0 (Baseline visit) ^a
6 Weeks	$28 < \text{STUDY DAY} \leq 56$
12 Weeks	$70 \leq \text{STUDY DAY} \leq 98$
18 Weeks	$112 \leq \text{STUDY DAY} \leq 140$
24 Weeks	$154 \leq \text{STUDY DAY} \leq 182$
30 Weeks	$196 \leq \text{STUDY DAY} \leq 224$
36 Weeks	$238 \leq \text{STUDY DAY} \leq 266$
42 Weeks	$280 \leq \text{STUDY DAY} \leq 308$

Cancer history	
Incomplete dates for cancer history (initial cancer diagnosis date and date of documented, locally advanced, inoperable or metastatic disease diagnosis) will be imputed as follows:
 
• If the day is missing, it will be imputed to the 15th day of the month.• If both day and month are missing and the year is prior to the year of the index date, the month and day will be imputed as July 1st.• If both day and month are missing and the year is same as the year of the index date, the month and day will be imputed as January 1st.• If the date is completely missing, no imputation will be performed.
Adverse events	
Incomplete AE dates will be imputed as follows:
 
• If the AE onset date is missing completely, then the onset date will be replaced by the index date.• If only the day part of the AE onset date is missing, but the month and year are equal to the index date, then the AE onset date will be replaced by the start of study treatment. For example, if the AE onset date is --/JAN/2015, and the index date is 15/JAN/2015, then the imputed AE onset date will be 15/JAN/2015. If the end date or resolution date indicates that the AE has stopped before the index date, this date will be used for imputation instead of the index date.

	
• If both the day and month of the AE onset date are missing but the onset year is equal to the index date, then the onset date will be replaced by the index date. For example, if AE onset date is --/---/2014, and the index date is 19/NOV/2014, then the imputed AE onset date will be 19/NOV/2014.• In all other cases the missing onset day or missing onset month will be replaced by 1.• Incomplete stop date will be replaced by the last day of the month (if day is missing only), if not resulting in a date later than the date of participant's death. In the latter case the date of death will be used to impute the incomplete stop date.• In all other cases the incomplete stop date will not be imputed. If stop date of AE is after date of cut-off this date will not be imputed and the outcome of the event will be "Not recovered/not resolved" (i.e. ongoing).
Previous and concomitant medication	
Incomplete prior/concomitant medication start and stop dates will be imputed as follows:
 
• If the medication start date is missing completely, then the medication start date will be replaced by the index date.• If the day of medication start date is missing, but the month and year are equal to the index date, then the medication start date will be replaced by the index date. For example, if the medication start date is --/JAN/2015, and the index date is 15/JAN/2015, then the imputed medication start date will be 15/JAN/2015.• If both the day and month of medication start date are missing but the start year is equal to the index date, then the medication start date will be replaced by the index date. For example, if the medication start date is --/---/2014, and the index date is 19/NOV/2014, then the imputed medication start date will be 19/NOV/2014.• In all other cases the missing medication day or missing medication month will be replaced by 1. Incomplete stop date will be replaced by the last day of the month (if day is missing only), if not resulting in a date later than the date of participant's death. In the latter case the date of death will be used to impute the incomplete stop date.• In all other cases the incomplete medication stop date will not be imputed. 
In case an imputed medication start date is later than the medication stop date, it will be replaced by the medication stop date.

Table 1 **Stopping rules for medication/procedure end dates**

End date of medication/procedure			Stopping rule
Day	Month	Year	
Unknown (UNK)	UNK	UNK	After index date (ongoing)
UNK	UNK	< Index date (year)	Before index date
UNK	UNK	>= Index date (year)	After index date
		< Index date (month and year)	Before index date
UNK		>= Index date (month and year)	After index date
		< Index date (complete date)	Before index date
		>= Index date (complete date)	After index date

UNK = Unknown

Table 2 **Rules to define previous and/or concomitant medications**

Start date of medication/procedure			Stopping rule (see Table 1)	Medication/procedure
Day	Month	Year		
UNK	UNK	UNK	Before index date	Previous
UNK	UNK	UNK	After index date	Previous and concomitant
UNK	UNK	<= Index date (year)	Before index date	Previous
UNK	UNK	<= Index date (year)	After index date	Previous and concomitant
UNK	UNK	> Index date (year) and <= Treatment end [+ 30] days (year)	After index date	Concomitant
UNK		<= Index date (month and year)	Before index date	Previous
UNK		<= Index date (month and year)	After index date	Previous and concomitant
UNK		> Index date (month and year) and <= last Avelumab/Axitinib (whichever comes later) [+ 30] days (month and year)	After index date	Concomitant
		<= Index date (date)	Before index date	Previous
		<= Index date (date)	After index date	Previous and concomitant
		> Index date (date) and <= last Avelumab/Axitinib (whichever comes later) [+ 30] days (date)	After index date	Concomitant

UNK = Unknown

Dates of study treatment	
 No imputation will be done for start date (index date will be present for all patients). 
End date of study treatments:
 
 In case the last date of study drugs is missing or incomplete the date of last administration of study drugs will be taken from the treatment termination eCRF pages.
--------------------------	---

	
 • If the last date of study drugs is completely missing and there is no EOT eCRF page and no death date the participant should be considered to be ongoing and use the cut-off date for the analysis as the last dosing date. • If the last date of study drugs is completely or partially missing and there is EITHER an EOT eCRF page or a death date available (within the cut-off date) then imputed last dose date is: 
 = 31DECYYYY, if only Year is available and Year < Year of min (EOT date, death date) = Last day of the month, if both Year and Month are available and Year = Year of min (EOT date, death date) and Month < the month of min (EOT date, death date) = min (EOT date, death date), for all other cases
Death date	
For survival analyses partially missing death dates will be imputed as follows:
 
If only the day is missing, the death date will be imputed to the maximum of the (non-imputed) day after the date of last contact and the 15th day of the month.
 
Otherwise it will not be imputed.

Tumor assessments	
Tumor assessment must be completed with day, month and year.
 
If measurement date for an evaluation have no day recorded, the 1st of the month is used.
 
If the month is not completed, the respective assessment will be considered to be at the date which is exactly between the previous and the following assessment. If both a previous and following assessments are not available, this assessment will not be used for any calculations.

Dates of subsequent anti-cancer therapy	
Incomplete dates for start date of subsequent anti-cancer therapy (drug therapy, radiation, other) will be imputed as follows:
 
 • If only day is missing, it will be imputed as the last day of the month unless the end date of subsequent anti-cancer therapy is before that date. In that case, the incomplete anti-cancer therapy start date will be imputed as the end date of the anti-cancer therapy.

	
• If both day and month are missing, no imputation will be performed. 
Incomplete subsequent anti-cancer therapy stop dates will not be imputed.

--	--

